10. APPENDICES

Appendix 1. DATA DERIVATION DETAILS

Appendix 1.1. Definition and Use of Visit Windows in Reporting

There were no visit windows defined for Study A0221047. The target observation of “Week 12 from Day 1 of Study A0221047” will also be that taken at a time closest to when the scheduled visit should have occurred.

Visit windows for after Study A0221109 are defined.

Table 4. Visit Windows for Efficacy Endpoints

Visit Label	Endpoint	Definition [Day window]
A0221047:Day1	Urodynamic Assessments Bladder Diary	Same definitions of A0221047 will be used.
A0221047:Week12	Urodynamic Assessments Bladder Diary	Same definitions of A0221047 will be used.
A0221047:Week52/ A0221109:Week28	(for Fesoterodine arms in Study A0221047) Urodynamic Assessments Bladder Diary	= An assessment where ‘Date of assessment’ – ‘Date Day 1 of Study A0221047’ + 1 = [310, 407]
A0221047:Week 64/ A0221109:Week40	(for Oxybutynin arm in Study A0221047) Urodynamic Assessments Bladder Diary	= An assessment where ‘Date of assessment’ – ‘Date Day 1 of Study A0221047’ + 1 = [408, 491]
Final Visit	Urodynamic Assessments Bladder Diary	= The last assessment where ‘Date of assessment’ – ‘Date Day 1 of Study A0221047’ + 1 > 169

Table 5. Visit Windows for Safety Endpoints

Visit Label	Endpoint	Definition [Day window]
A0221047:Week24/ A0221109:Day1	Vital Signs Visual Acuity and Accommodation PVR Clinical Laboratory Evaluation CBCL GPT	= An assessment where 'Date of assessment' – 'Date Week 0 of Study A0221109' + 1 is in [-20, 42]
A0221047:Week36/ A0221109:Week12	Vital Signs Visual Acuity and Accommodation PVR Clinical Laboratory Evaluation CBCL GPT	= An assessment where 'Date of assessment' – 'Date Week 0 of Study A0221109' + 1 is in [43, 140]
A0221047:Week52/ A0221109:Week28	Vital Signs Visual Acuity and Accommodation PVR Clinical Laboratory Evaluation CBCL GPT	= An assessment where 'Date of assessment' – 'Date Week 0 of Study A0221109' + 1 is in [141, 238]
A0221047:Week64/ A0221109:Week40	(for Oxybutynin arm in Study A0221047) Vital Signs Visual Acuity and Accommodation PVR Clinical Laboratory Evaluation CBCL GPT	= An assessment where 'Date of assessment' – 'Date Week 0 of Study A0221109' + 1 is in [239, 322]
Final Visit	Vital Signs Visual Acuity and Accommodation PVR Clinical Laboratory Evaluation CBCL GPT	= The last assessment after 'Date of assessment' – 'Date Week 0 of Study A0221109' + 1 >= 43

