Assess Study Medication compliance	X ^a		X			X	

a. The Week 0 visit of Study A0221109 is the same visit as Week 24 visit of Study A0221047. All procedures done at Week 24 visit of Study A0221047 will be used as the Week 0 data for Study A0221109. These procedures (Study A0221047 procedures) will not be repeated at Week 0 of Study A0221109.

b. Or in the event of the subject withdrawing early from the study. Urodynamic assessment should only be performed in subjects who have not missed any doses in the 3 days prior to the visit.

c. Telephone calls may be substituted by a clinic visit at the discretion of the investigator.

d. If vital signs or physical examinations show a clinically relevant change from baseline of the precedent Study A0221047, then safety monitoring will occur at a minimum of monthly intervals, or more frequently as clinically appropriate, until the abnormality resolves.

e. PVR only in subjects who are not performing intermittent catheterization or in any subjects who have >1 urinary tract infection (UTI) during the study.

f. Laboratory assessments may be repeated as needed to follow-up on significant findings.

g. Urinalysis: Urine microscopy, culture, and sensitivity to be performed in the event of the presence of symptoms (eg, fever, flank pain), positive leucocytes and/or nitrites on urinalysis, or if the subject has a documented history of vesicoureteral reflux (VUR).

h. Only for female subjects of child-bearing potential. Pregnancy tests may also be repeated as per request of Institutional Review Board (IRB)/Ethics Committee (EC) or if required by local regulations.

i. The bladder diary will be completed for 3 days prior to Final Visit.

j. The dosing log will be completed on a daily basis.

k. At Final Visit, the time of last dose should be recorded.

l. Follow up visit will be done at 4 weeks after Final Visit.

Table 2. Subjects who were randomized to Oxybutynin arm in Study A0221047

Visit	Visit 1	Visit 2	Visit 3	Visit 4	Visit 5	Visit 6	Visit 7	Final Visit ^b	Follow-Up Visit ^l
Week (Weeks from baseline of the precedent Study A0221047)	Week 0 (24)	Week 6 (30)	Week 12 (36)	Week 18 (42)	Week 24 (48)	Week 28 (52)	Week 34 (58)	Week 40 (64)	Week 44 (68)
Allowance (weeks)	-	±2	±2	±2	±2	±2	±2	±2	+2
Clinic visit/Phone call	Clinic visit	Phone call ^c	Clinic visit	Phone call ^c	Phone call ^c	Clinic visit	Phone call ^c	Clinic visit	Phone call ^c
Informed Consent & Assent	X								
Demography	X								

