6.4. Subject Withdrawal

If treatment is inadequate or the subject cannot tolerate the dose of fesoterodine, consideration should be given to withdrawal.

Subjects may withdraw from the study at any time at their own, or their legal representative(s) request, or they may be withdrawn at any time at the discretion of the investigator or sponsor for safety or behavioral reasons, or the inability of the subject to comply with the protocol required schedule of study visits or procedures at a given study site.

If a subject does not return for a scheduled visit, every effort should be made to contact the subject. All attempts to contact the subject and information received during contact attempts must be documented in the subject's medical record. In any circumstance, every effort should be made to document subject outcome, if possible. The investigator should inquire about the reason for withdrawal, request the subject to return all unused investigational product(s), request the subject to return for a final visit, if applicable, and follow-up with the subject regarding any unresolved AEs.

If a subject withdraws from the study prior to Final visit (Week 28 in subjects who were randomized to Fesoterodine arms in Study A0221047, or Week 40 in subjects who were randomized to Oxybutinin arm in Study A0221047), the same assessments as at Final

visit should be performed if possible. Urodynamic assessment should only be performed in subjects who have not missed any doses in the 3 days prior to the visit.

Subjects who withdraw early from the study and who have taken at least 1 dose of study medication should also be contacted by telephone approximately 4 weeks after stopping study medication, and have the same assessments performed as at Follow-up visit.

If the subject withdraws from the study, and they or their legal representative(s) also withdraw consent for disclosure of future information, no further evaluations should be performed, and no additional data should be collected. The sponsor may retain and continue to use any data collected before such withdrawal of consent.

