5.3. Safety Analysis Set

The Safety Analysis Set will include all subjects who have been enrolled and received at least one dose of study medication in Study A0221109.

For analyses of adverse events, the data from Study A0221047 and Study A0221109 will be merged (see the details in [Section 8.1](#)).

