7. HANDLING OF MISSING VALUES

No imputation for missing data will be planned in efficacy and safety analysis.

In the case that the data of patient's background in Study A0221047 is used for the analysis of this study, handling of missing data in Study A0221047 will be employed in this study.

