8. STATISTICAL METHODOLOGY AND STATISTICAL ANALYSES

8.1. Statistical Methods

Efficacy endpoints and treatment-emergent adverse events will be summarized using merged data of Study A0221047 and Study A0221109. When the longitudinal changes are analyzed for the merged data, baseline will be Visit 1 (Screening) or Visit 2 (Day 1) of Study A0221047. Demographics and baseline characteristics including medical history, prior drug/Non-drug treatments will use baseline information at Visit 1 (Screening) or Visit 2 (Day 1) of Study A0221047. Other safety endpoints will be summarized for the data of Study A0221109 alone, and baseline will be Week 0 of Study A0221109.

Treatments will be labeled as follows:

Cohorts of Study A0221047 (for analysis using the merged data of Study A0221047 and A0221109)

Cohort 1

Cohort 2

Treatment groups of Study A0221047 (for analysis using the merged data of Study A0221047 and A0221109, demographics and baseline characteristics)

Fesoterodine 4 mg Tab

Fesoterodine 8 mg Tab

Oxybutynin->Fesoterodine 4 mg Tab

Oxybutynin->Fesoterodine 8 mg Tab

Fesoterodine 2 mg BIC

Fesoterodine 4 mg BIC

Treatment group at baseline in Study A0221109 (for analysis using the data of Study A0221109 alone)

Fesoterodine 4 mg Tab (A0221109)

Fesoterodine 8 mg Tab (A0221109)

Fesoterodine 2 mg BIC (A0221109)

Fesoterodine 4 mg BIC (A0221109)

The cohorts and the treatment groups of Study A0221047 will be used for data summaries of efficacy endpoints and treatment-emergent adverse events. The treatment groups at baseline in Study A0221109 will be used for data summaries of the safety endpoints excluding adverse events, although the dosage can be reduced to the lower dose at each clinic visit for subjects on the higher dose.

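### SAP Table 5 starts the safety Final Visit at extension Day 43, so a withdrawal assessment on Days 2 to 42 falls only in the Day 1 row

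*SAP*

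**What the plan says.** SAP 8.1 sets the frame for vital signs, vision, PVR, laboratory tests, CBCL and GPT: "Other safety endpoints will be summarized for the data of Study A0221109 alone, and baseline will be Week 0 of Study A0221109". SAP 8.2.2 then summarises these measures and their changes from baseline by visit.

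Table 5 of SAP Appendix 1.1 assigns assessments to visits by extension day, with Week 0 as Day 1:

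- **Day 1 row:** "Date Week 0 of Study A0221109' + 1 is in [-20, 42" (both ends included).
- **Week 12, Week 28, Week 40:** [43, 140], [141, 238] and [239, 322].
- **Final Visit:** the last assessment with "Date Week 0 of Study A0221109' + 1 >= 43".

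Table 4 does the same for urodynamics and the bladder diary. Its Final Visit is the last assessment with "Date Day 1 of Study A0221047’ + 1 > 169", counted from Day 1 of A0221047.

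Protocol 6.4 covers early leavers: "If a subject withdraws from the study prior to Final visit", the Final Visit assessments should be done where possible. Footnote b to the Final Visit column of the schedule agrees: "Or in the event of the subject withdrawing early from the study". Neither sets a minimum time on treatment. SAP 5.3 reads "The Safety Analysis Set will include all subjects who have been enrolled" and requires only one dose in the extension. SAP 7 states: "No imputation for missing data will be planned in efficacy and safety analysis".

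**The concern.** A last-assessment row is useful mainly for children who miss the scheduled final visit. With a floor at Day 43, it leaves out the earliest of them. A withdrawal assessment dated Days 2 to 42 was collected because the protocol asked for it, and it comes from a child in the Safety Analysis Set. Yet it meets only the rule for a row labelled Day 1, so it enters neither the Final Visit summary nor any change-from-baseline summary.

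Safety and tolerability are the primary objective, and the values left out would come from the children who stopped soonest. The efficacy table has no such floor. One withdrawal visit could therefore count as Final Visit for the secondary objective and not for the primary one.

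**Working it through.** **1. Reproduce the Table 5 cut points.** Nominal extension day = 7 × week + 1, so Weeks 0, 12, 28 and 40 are Days 1, 85, 197 and 281. The midpoints are:

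- (1 + 85)/2 = 43
- (85 + 197)/2 = 141
- (197 + 281)/2 = 239

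These match the table. The earliest in-window Week 12 visit is Day 85 − 14 = Day 71, so no on-schedule visit is mislabelled.

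**2. Classify Days 2 to 42.** Each of these 42 − 2 + 1 = 41 days meets the Day 1 rule and no other. Day 43 is the first day that counts as Week 12 or as Final Visit. The current Final Visit rule captures 0 of the 41 days.

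**3. Compare with Table 4.** Extension Week 0 is the Week 24 visit of A0221047, nominally Day 24 × 7 + 1 = 169. A day count above 169 is then extension Day 2 onward, and extension Days 2 to 42 are A0221047 Days 170 to 210. Table 4 accepts all 41. The visit allowance of A0221047 is not in the documents, so the actual date of Week 0 is an assumption:

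| Week 0 on A0221047 day | Days 2–42 accepted by Table 4 |
|---|---|
| 155 | 27 of 41 (from Day 16) |
| 162 | 34 of 41 (from Day 9) |
| 168 | 40 of 41 (from Day 3) |
| 169 or later | 41 of 41 |

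**4. What data could arise on these days.** The Week 6 contact covers only concomitant medication, adverse events and the dosing log. Only early-withdrawal assessments and unscheduled or repeat tests are affected.

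**5. Likely number of children.** Protocol 9.1 assumes 12.5% drop-out in A0221047 (24 weeks, 168 days) and about 9 children here. As an illustration, apply a drop-out of D per 168 days at a constant rate. The probability per child is p = 1 − (1 − D)^(41/168). The expected number is 9p, and the chance of at least one is 1 − (1 − p)^9. Because the protocol asks for these assessments only where possible, the last column halves p.

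| D | p | 9p | At least one, all assessed | At least one, half assessed |
|---|---|---|---|---|
| 6.25% | 0.0156 | 0.14 | 13% | 7% |
| 12.5% | 0.0321 | 0.29 | 25% | 14% |
| 25% (stress case, not supported by the documents) | 0.0678 | 0.61 | 47% | 27% |

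Entrants have completed 24 weeks and, as a rule, tolerated their dose, so the lower figures are more plausible. One child is 1/9 = 11% of the expected total. The share within its own table column would be larger, because these measures are summarised by treatment group, with up to four groups.

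**The case against.** The strongest reply is that the two tables serve different schedules. In the extension, urodynamics and diary are taken only at the Final Visit, so Table 4 needs only to separate extension data from A0221047 data. Safety measures are also taken at Week 12, and Table 5 starts its Final Visit where the first post-baseline window starts. Different limits are not in themselves a contradiction, and a minimum exposure could be argued for under an objective of long-term treatment. That much is fair. But the SAP gives no rationale for a floor, and a midpoint that separates two scheduled visits is no reason to restrict a last-assessment row.

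The contrast with Table 4 also has limits. It covers all 41 days only if Week 0 falls on Day 169 or later. Urodynamics at withdrawal require three days without a missed dose, and an unplanned withdrawal may leave no diary. The Table 5 gap stands without the comparison.

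The baseline value is not in doubt, because SAP 8.1 fixes it at Week 0 and those procedures are not repeated. Redefining the Day 1 row therefore does not change baseline. It does keep on-treatment values out of a row labelled Day 1, where the SAP has no rule for two values in one window.

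The data survive elsewhere. A test result that leads to discontinuation is reportable as an AE (Protocol 8.5), laboratory abnormalities are tabulated for any time in the study, listings are planned, and each child has a narrative. In a descriptive study of about 9 children these carry much of the evidence. This limits the consequence but does not make the rule right.

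**Conclusion.** The concern holds. As written, Table 5 gives a safety assessment on extension Days 2 to 42 no post-baseline row, although the protocol asks for that assessment at withdrawal and the child is in the Safety Analysis Set. What is lost is mainly the by-visit and Final Visit value of a child whose result did not itself drive the withdrawal.

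The expected impact is low: possibly no child, and a 7% to 25% chance of at least one under the 6.25% and 12.5% drop-out assumptions. Those figures borrow another study's planning rate, assume it is constant, and vary the share of leavers who are assessed. The Week 12, 28 and 40 windows are sound. Because the affected summaries serve the primary objective and the correction is cheap, it should be made.

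**What to change.** Change two definitions in SAP Table 5:

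1. **Day 1 row:** the Week 0 visit record, meaning the A0221047 Week 24 visit procedures on whatever date they were completed, in line with SAP 8.1. It should not take any assessment up to Day 42.
2. **Safety Final Visit:** for each endpoint separately, the last assessment after the Week 0 visit, excluding Week 0 procedures, in place of the Day 43 floor.

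Leave the Week 12, 28 and 40 windows as they are. Any endpoint with a value on Day 43 or later keeps the same Final Visit value.

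There is one small downside. If an unscheduled early test is an endpoint's only value after Week 0, it becomes that endpoint's Final Visit value and is pooled with later ones. The listing should flag such cases.

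The cost is two limits in one table, one listing flag and the matching program change. No new data are needed.

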This is an extension study for the subjects who completed Study A0221047 in Japan, and the primary objective is to investigate the safety and tolerability of fesoterodine for these subjects. No statistical testing will be planned but descriptive statistics will be used along with subject narratives. Therefore, the number of subjects to be enrolled in this study is not based on any formal sample size calculation.

In Study A0221047, a few Japanese subjects in cohort 1 (body weight >25 kg) and 9 Japanese subjects in cohort 2 (body weight ≤25 kg) are planned to be enrolled as potential candidate subjects for this study. Assuming a 12.5% drop-out rate in Study A0221047, out of Japanese subjects who are enrolled to Study A0221047, approximately 9 subjects are expected to be enrolled in this study.

SCHEDULE OF ACTIVITIES

The schedule of activities table provides an overview of the protocol visits and procedures. Refer to the Study Procedures and Assessments sections of the protocol for detailed information on each procedure and assessment required for compliance with the protocol.

The investigator may schedule visits (unplanned visits) in addition to those listed on the schedule of activities, in order to conduct evaluations or assessments required to protect the well-being of the subject.

Table 1. Subjects who were randomized to Fesoterodine arms in Study A0221047

Visit	Visit 1	Visit 2	Visit 3	Visit 4	Visit 5	Final Visit ^b	Follow-Up Visit ^l
Week (Weeks from baseline of the precedent Study A0221047)	Week 0 (24)	Week 6 (30)	Week 12 (36)	Week 18 (42)	Week 24 (48)	Week 28 (52)	Week 32 (56)
Allowance (weeks)	-	±2	±2	±2	±2	±2	+2
Clinic visit/Phone call	Clinic visit	Phone call ^c	Clinic visit	Phone call ^c	Phone call ^c	Clinic visit	Phone call ^c
Informed Consent & Assent	X						
Demography	X						
Review Concomitant Medications	X ^a	X	X	X	X	X	X
Adverse Event Monitoring	X ^a	X	X	X	X	X	X
Child Behavior Checklist	X ^a		X			X	
Grooved Pegboard Test	X ^a		X			X	
Vital Signs ^d	X ^a		X			X	
Weight	X ^a		X			X	
Physical Examination ^d	X ^a		X			X	
Visual acuity and accommodation	X ^a		X			X	
Post-void residual volume (PVR) ^e	X ^a		X			X	
Laboratory ^f							
Hematology	X ^a		X			X	
Blood Chemistry	X ^a		X			X	
Urinalysis ^g	X ^a		X			X	
Urine Pregnancy Test ^h	X ^a		X			X	
Urodynamic Studies						X	
Bladder diary ⁱ						X	
Dosing log ^j	X ^a	X	X	X	X	X ^k	
Study Medication Dispensed	X		X				
Study Medication return/count	X ^a		X			X	

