3.1. Study Visits

There will be the following clinic visits:

Subjects who were randomized to Fesoterodine arms in active comparator/efficacy phase in Study A0221047

- Visit 1 (Week 0 [Week 24 in Study A0221047])
- Visit 3 (Week 12)
- Final Visit (Week 28)

Subjects who were randomized to Oxybutynin arms in active comparator phase in Study A0221047

- Visit 1 (Week 0 [Week 24 in Study A0221047])

- Visit 3 (Week 12)
- Visit 6 (Week 28)
- Final Visit (Week 40)

The Week 0 visit of Study A0221109 is the same visit as Week 24 visit of the precedent Study A0221047. All procedures done at Week 24 visit of Study A0221047 will be used as the Week 0 data for Study A0221109.

There will also be a minimum of 3 or 4 telephone calls (or clinic visits) to subjects to identify any new adverse events, review concomitant medication usage and the dosing log at the following telephone calls (or clinic visits).

Subjects who were randomized to Fesoterodine arms in active comparator/efficacy phase in Study A0221047

- Visit 2 (Week 6)
- Visit 4 (Week 18)
- Visit 5 (Week 24)

Subjects who were randomized to Oxybutynin arms in active comparator phase in Study A0221047

- Visit 2 (Week 6)
- Visit 4 (Week 18)
- Visit 5 (Week 24)
- Visit 7 (Week 34)

And there will be a further telephone call (or clinic visit) at:

- Follow-up Visit. To review ongoing or new adverse events, review concomitant medications for subjects 4 weeks after Final Visit. It will also be completed for all subjects who withdraw early from the study and take at least 1 dose of study medication in the A0221109 study.

Other contacts (for example, telephone calls or unscheduled clinic visits) may also be made, as appropriate, to verify study medication dose, and to provide reminders to the subject to complete daily dosing log, if needed.

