5.3. Drug Supplies

5.3.1. Dosage Form(s) and Packaging

For subjects who was assigned to Cohort 1 (subjects >25 kg) in the precedent Study A0221047, fesoterodine PR 4 mg and 8 mg will be provided by Pfizer as tablets. Both the 4 mg and 8 mg dosage forms are tablets designed for oral administration. The tablets should be taken orally with water without chewing. The study medication is a blue, oval tablet.

For subjects who was assigned to Cohort 2 (subjects \leq 25 kg) in the precedent Study A0221047, fesoterodine 2 mg and 4 mg once daily will be provided by Pfizer as a BIC formulation. Both dosage forms are capsules designed for oral administration. The capsules should be taken orally with water without chewing. For subjects who cannot swallow whole capsules, the capsule may be opened and the beads sprinkled on a suitable medium (eg, apple sauce) as directed by the investigator or approved representative (eg, pharmacist).

At each clinic visit except for Final Visit, subjects will be provided study medication.

Subjects >25 kg who cannot swallow tablets are not permitted to take the BIC formulation and are excluded from the study.

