7.2. Safety Assessments

7.2.1. Vital Signs

Blood pressure, temperature and pulse rate should be measured at each clinic visit. This schedule of measurements should provide adequate indication of any clinically relevant changes. However, if vital signs show a clinically relevant change from baseline of Study A0221047, then safety monitoring will occur at a minimum of monthly intervals, or more frequently as clinically appropriate, until the abnormality resolves. The measured results will be assessed in the context of age appropriate norms.

Temperature may be taken via oral, tympanic or axillary routes as per local accepted practice. Digital devices are permitted; however, mercury thermometers should not be

used. The same method as Study A0221047 should be used for the subject throughout the study.

Blood pressure should be measured using a pediatric or appropriately sized sphygmomanometer in the sitting/resting position with the subject's arm supported at the level of the heart, and recorded to the nearest mmHg. The same arm (preferably the dominant arm) as Study A0221047 will be used throughout the study.

The same size blood pressure cuff as Study A0221047, which has been properly sized and calibrated, will be used to measure blood pressure each time. The use of automated devices for measuring blood pressure and pulse rate are acceptable, although, when done manually, pulse rate will be measured in the brachial/radial artery for at least 30 seconds.

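### The safety Final Visit in SAP Table 5 has no upper day and no link to last dose, so an off-drug recheck of an abnormality found at the last visit can replace the end-of-treatment value

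*SAP*

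**What the plan says.** SAP Table 5 covers vital signs, visual acuity and accommodation, PVR, laboratory tests, CBCL and GPT. Study day is the assessment date minus the Week 0 date of A0221109, plus 1. The by-visit windows are bounded: Week 12 is [43, 140], Week 28 is [141, 238], and Week 40 (former oxybutynin children) is [239, 322]. The Final Visit row is open-ended: "The last assessment after 'Date of assessment" minus the Week 0 date, plus 1, reaches 43 or more. SAP 8.2.2 summarises these measures by visit using A0221109 data alone.

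Four parts of the protocol bear on which assessment is last:

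- **Rechecks.** After a clinically relevant change in vital signs, "safety monitoring will occur at a minimum of monthly intervals, or more frequently as clinically appropriate, until the abnormality resolves" (7.2.1). Section 7.2.2 has the same rule for the physical examination, whose list of systems includes visual acuity and accommodation. For laboratory tests the rule is looser: "Laboratory assessments may be repeated as needed to follow-up on significant findings" (Schedule of Activities, footnote f). More generally, "The investigator may schedule visits (unplanned visits) in addition to those listed on the schedule of activities".
- **End of drug supply.** "At each clinic visit except for Final Visit, subjects will be provided study medication" (5.3.1).
- **Withdrawal.** The investigator should "request the subject to return for a final visit, if applicable" (6.4). Urodynamics at that visit is limited to children who missed no doses in the previous 3 days. The safety tests have no such condition.
- **Scheduled follow-up.** Its content is "To review ongoing or new adverse events, review concomitant medications for subjects 4 weeks after Final Visit" (3.1).

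**The concern.** Safety and tolerability are the primary objective, and a reader will take the Final Visit row as the state of the children at the end of treatment. Table 5 does not guarantee that. A child with normal findings has no reason to return after the scheduled Final Visit, so that child's value stays on drug. A child with a relevant change in pulse, blood pressure or vision at that visit is asked back until it resolves. The child has no further study drug, and the last of those returns becomes the summarised value. Under this route the selection depends on the outcome and pulls the end-of-treatment summary towards no change. In groups of a few children, one such substitution is visible in the mean.

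**Working it through.** **1. Reproduce the windows.** Target day = 7 × week + 1, so Weeks 0, 12, 28 and 40 fall on Days 1, 85, 197 and 281. Lower bounds are the midpoints between targets: (1 + 85)/2 = 43; (85 + 197)/2 = 141; (197 + 281)/2 = 239. The Week 40 upper bound is 281 + 42 − 1 = 322, where 42 = (281 − 197)/2. All agree with Table 5, so the day arithmetic is sound. Only the Final Visit row lacks an upper limit.

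**2. Which assessment becomes Final Visit?** Three cases:

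- *Abnormal at Week 12, rechecked monthly until resolved.* The scheduled Week 28 or Week 40 visit is still to come and is on drug. Provided nothing is measured after it, it is the last assessment, and Final Visit is correct.
- *Abnormal at the scheduled Final Visit (about Day 197, or Day 281 for former oxybutynin children) or at the early-withdrawal visit, then rechecked.* The recheck is later and becomes Final Visit. No drug is dispensed at the Final Visit, so it is off drug.
- *Drug stopped, child returns some time later for the withdrawal assessments.* If on or after Day 43, these off-drug values are the Final Visit values.

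**3. Do the bounded windows keep the recheck out?** Assume the last dose is at the scheduled Final Visit, apply the protocol's ±14-day allowance, and place a recheck 28 days later:

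| Children | Final Visit day | Days left in window | Recheck day | Inside window? |
|---|---|---|---|---|
| Fesoterodine arms, upper bound 238 | 183 | 55 | 211 | yes |
| | 197 | 41 | 225 | yes |
| | 211 | 27 | 239 | no |
| Former oxybutynin, upper bound 322 | 267 | 55 | 295 | yes |
| | 281 | 41 | 309 | yes |
| | 295 | 27 | 323 | no |

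The window can therefore hold both the on-drug value and the first off-drug recheck. Appendix 1.1 states a closest-to-schedule rule, but words it for Week 12 of A0221047. For A0221109 it gives no rule for choosing among several assessments in a window. Capping Final Visit at 238 or 322 would not solve the problem either, because four of the six rechecks above fall below the cap.

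**4. Size.** If one child's value is replaced, the group mean moves by (difference between that child's two values)/n. The protocol (9.1) expects about 9 children, and SAP 8.1 uses four treatment groups for these summaries. With 2 to 5 children per group (assumption), the shift is 1/2 = 50% to 1/5 = 20% of that difference. As an illustration only, take a child with pulse +25 bpm at the scheduled visit and 0 at the recheck. The group mean change falls by 25/2 = 12.5 bpm to 25/5 = 5 bpm. Across all 9 children the share would be 1/9, about 11%.

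**The case against.** The best defence is that the situation is uncommon and the abnormality remains visible elsewhere. Much of that stands.

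- A reader might infer that every child with an abnormal finding is summarised at a resolved value. The documents do not support that: a Week 12 abnormality is normally superseded by a later scheduled on-drug visit.
- A reader might infer that all six Table 5 measures are followed until normal. The until-resolved rule covers vital signs and the physical examination, with vision included through the latter. Laboratory repeats are as needed, and PVR, CBCL and GPT have no such rule.
- A reader might think the Week 32 or Week 44 follow-up feeds off-drug data into the windows. It collects only adverse events and concomitant medications, so contamination needs an unplanned visit or a late withdrawal visit.
- For the Week 28 and Week 40 rows, substitution is possible but not shown, because no last-value rule is stated there.
- Abnormal findings that meet the protocol's criteria become adverse events. The plan also has by-visit rows, listings, a narrative for each child and an any-time laboratory abnormality table. The SAP text describes no any-time table for vital signs, vision or PVR, but safety outputs also follow sponsor standards that are not reproduced in it.

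None of this makes the Final Visit row right. It is a stated rule that selects the wrong assessment in an identifiable situation, and the other outputs do not correct that row.

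**Conclusion.** The point holds in a limited form. Table 5 lets an off-drug assessment stand as the safety Final Visit when an abnormality found at the last scheduled visit or at withdrawal is rechecked, or when the withdrawal visit itself is late. For vital signs and vision under the recheck route, the direction is systematic, towards no change. For the other measures and for late withdrawal visits, the direction depends on whether the effect fades off drug, and the documents give no time course for that.

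Each substitution is worth 20% to 50% of the difference between that child's two values in the group mean, assuming 2 to 5 children per group. The documents do not say how often post-treatment rechecks will occur, so the expected bias cannot be stated, and few children are likely to be involved. The row should be corrected, but the documents do not support concluding that the safety assessment as a whole would miss these events.

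**What to change.** In SAP Appendix 1.1, Table 5:

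1. Define the safety Final Visit as the scheduled Final Visit or the early-withdrawal assessment, and exclude later unscheduled rechecks from that row.
2. For the Week 28 and Week 40 windows, state that the scheduled assessment is used, or the one closest to the target day, in preference to a post-treatment recheck.
3. Use the last-dose date to flag assessments made after treatment stopped. Show later rechecks, and withdrawal assessments made well after the last dose, as off-treatment in a separate row or listing.

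It is tempting to borrow the urodynamic condition (no missed doses in the 3 days before the visit) as an exclusion. That would drop children who stopped for an adverse event and returned later. With no imputation planned (SAP 7), it would remove informative tolerability cases from the summary. Showing them separately avoids this.

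The cost is a few lines of SAP text and a small programming change. The time of last dose and the daily dosing log are already collected, so no new data are needed. The only downside is that some values appear in a separate row or listing.
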